9.5. Pharmacokinetics

At the visits and times specified in the Schedule of Activities (Section 2), venous blood samples of approximately 4 mL each will be collected to determine the plasma concentrations of LY3375880. The actual date and time (24-hour clock time) of each dose and PK sampling blood draw will be recorded. It is essential that the actual times of dosing and sampling are recorded accurately. In addition, subjects who were deemed responders at Week 16 may be prompted to collect a PK sample at the first scheduled where loss of response is observed (i.e., EASI-25 was not achieved) in the maintenance period. This will support the evaluation of ADA status at the time of retreatment for subjects randomized to placebo until loss of response during the maintenance period. To prevent unblinding of treatment regimen, all subjects who are deemed responders at Week 16 will have PK and immunogenicity collected upon loss of response.

In addition to the planned PK sampling as described, a maximum of 2 samples may be collected at additional time points during the study if warranted and agreed upon between both the investigator and sponsor. Instructions for the collection and handling of blood samples will be provided by the sponsor. The actual date and time [24-hour clock time] of each sampling will be recorded.

Drug concentration information that may unblind the study will not be reported to investigative sites or blinded personnel until the study has been unblinded.

Bioanalytical samples collected to measure IP concentration will be retained for a maximum of 1 year following the last subject visit for the study.

9.6. Pharmacodynamics

Samples collected (as specified in the schedule of activities) to measure TARC, Periostin, IL-19 will be identified by the subject number (coded) and retained at a facility selected by Lilly or its designee for a maximum of 1 year following the last subject visit for the study at a facility selected by Lilly or its designee.

9.7. Pharmacogenomics

9.7.1. Whole Blood Samples for Pharmacogenetic Research

A whole blood sample will be collected for pharmacogenetic analysis as specified in the Schedule of Activities (Section 2) where local regulations allow.

Samples will not be used to conduct unspecified disease or population genetic research either now or in the future. Samples will be used to investigate variable response to LY3375880 and to investigate genetic variants thought to play a role in AD or associated diseases. Assessment of variable response may include evaluation of AEs or differences in efficacy.

All samples will be coded with the subject number. These samples and any data generated can be linked back to the subject only by the investigator site personnel.

Samples will be retained at a facility selected by Lilly or its designee for a maximum of 15 years after the last subject visit for the study, or for a shorter period if local regulations and/or ERBs/investigational review boards impose shorter time limits. This retention period enables use of new technologies, response to regulatory questions, and investigation of variable response that may not be observed until later in the development of LY3375880 or after LY3375880 becomes commercially available.

Molecular technologies are expected to improve during the 15-year storage period and therefore cannot be specifically named. However, existing approaches include whole genome or exome sequencing, genome-wide association studies, and candidate gene studies. Regardless of technology utilized, genotyping data generated will be used only for the specific research scope described in this section.

9.8. Biomarkers

Biomarker research is performed to address questions of relevance to drug disposition, target engagement, pharmacodynamics (PD), mechanism of action, variability of subject response (including safety), and clinical outcome. Sample collection is incorporated into clinical studies to enable examination of these questions through measurement of biomolecules including DNA, RNA, proteins, lipids, and other cellular elements.

Samples for biomarker research (serum, plasma, whole blood RNA, whole blood for epigenetics, and skin biopsies for mRNA expression profiling and immunohistochemistry) will be collected at the times specified in the Schedule of Activities (Section 2) where local regulations allow. Blood samples for nonpharmacogenetic biomarker research will be collected at the times specified in the Schedule of Activities (Section 2) where local regulations allow.

Samples will be used for research on the drug target, disease process, variable response to LY3375880, pathways associated with AD or associated diseases, mechanism of action of LY3375880, and/or research method or in validating diagnostic tools or assay(s) related to AD or associated diseases.

Skin biopsy samples from AD lesions and adjacent nonlesional tissue will be collected and used to study biomarkers related to AD and/or related to the mechanism of action of LY3375880. Techniques used may include but are not limited to immunohistochemistry and microarray expression profiling. Samples may be used for exploratory microarray expression profiling or transcriptome sequencing. Detailed instructions for sample collection and handling will be provided by the sponsor. Samples will be sent to a sponsor-designated laboratory for immunohistochemistry.

All samples will be coded with the subject number. These samples and any data generated can be linked back to the subject only by the investigator site personnel.

Samples will be retained at a facility selected by Lilly or its designee for a maximum of 15 years after the last subject visit for the study, or for a shorter period if local regulations and ERBs impose shorter time limits. This retention period enables use of new technologies, response to regulatory questions, and investigation of variable response that may not be observed until later in the development of LY3375880 or after LY3375880 becomes commercially available.

9.9. Medical Resource Utilization and Health Economics

Health Economics and Medical Resource Utilization parameters will not be evaluated in this study.

10. Statistical Considerations

Approximately 200 subjects will be randomized at a 1:1:1:1 ratio in the blinded induction dosing period to LY3375880 50 mg, 150 mg, 600 mg, and placebo (50 subjects per dosing regimen).

Assuming 36% and 8% of subjects achieve an IGA score of 0 or 1 (clear or almost clear skin) and ≥ 2 -point improvement from baseline at Week 16 for LY3375880 and placebo, respectively, pairwise comparisons to placebo have at least 90% power using a 2-sided Fisher's exact test at the 0.05 significance level, with no adjustment for multiple comparisons.

10.1. Populations for Analyses

For purposes of analysis, the following populations are defined:

Population	Description
Enrolled	All participants who sign informed consent.
Safety	All randomized participants who take at least 1 dose of their assigned double-blind study treatment. Participants will be included in the treatment group they were randomized to.
Intent-to-Treat (ITT)	All randomized subjects, even if the subject does not take the assigned treatment, does not receive the correct treatment, or otherwise does not follow the protocol.
Maintenance Period	All ITT subjects who received at least 1 dose of study treatment and have entered the maintenance period at Week 16 (Visit 8).

10.2. Statistical Analyses

10.2.1. General Statistical Considerations

Statistical analysis of this study will be the responsibility of Lilly or its designee. A detailed SAP describing the statistical methodologies will be developed by Lilly or its designee.

Efficacy analyses will be conducted on the intent-to-treat (ITT) population. This set includes all randomized subjects, even if the subject does not take the assigned treatment, does not receive the correct treatment, or otherwise does not follow the protocol.

Safety analyses will be conducted on the safety population. This set includes all data from all randomized subjects receiving at least 1 dose of the IP according to the treatment to which the subjects were randomized.

When reported, descriptive statistics will include the number of subjects, mean, standard deviation, median, minimum, and maximum for continuous measures, and frequency counts and percentages for categorical measures.

Treatment comparisons of discrete efficacy variables between LY3375880 and placebo will be made using a logistic regression analysis with treatment, baseline disease severity (IGA 3 versus 4), geographic region, and, if applicable, baseline scores (such as baseline EASI score for a comparison of EASI-75) in the model. The percentages, difference in percentages, and 95% confidence interval (CI) of the difference in percentages will be reported. Treatment-by-region interaction will be added to the logistic regression model of the primary and key secondary

variables as a sensitivity analysis. If this interaction is significant at a 2-sided 0.1 level, further inspection will be used to assess whether the interaction is quantitative (i.e., the treatment effect is consistent in direction but not size of effect) or qualitative (the treatment is beneficial for some but not all regions).

When evaluating continuous measures over time, a restricted maximum likelihood-based mixed-effects model of repeated measures (MMRM) will be used. The model will include treatment, baseline disease severity, geographic region, visit, and treatment-by-visit interaction as fixed categorical effects and, if a baseline score for the measure is available, baseline score and baseline score-by-visit interaction as fixed continuous effects. An unstructured (co)variance structure will be used to model the between- and within-subject errors. If this analysis fails to converge, other structures will be tested. The Kenward–Roger method will be used to estimate the degrees of freedom. Type III sums of squares for the least squares means will be used for the statistical comparison; 95% CI will also be reported. Contrasts will be set up within the model to test treatment groups at specific time points of interest. Further details on the use of MMRM will be described in the SAP.

Fisher's exact test will be used for the AEs, discontinuation, and other categorical safety data for between-treatment group comparisons. Continuous vital signs and other continuous safety variables including laboratory variables will be analyzed by an analysis of covariance with treatment and baseline value in the model.

The Kaplan–Meier product limit method will be used to estimate the survival curves for time-to-event variables.

All tests of treatment effects will be conducted at a 2-sided alpha level of 0.05 with no control for multiple comparisons, unless otherwise stated.

Any change to the data analysis methods described in the protocol will require an amendment ONLY if it changes a principal feature of the protocol. Any other change to the data analysis methods described in the protocol, and the justification for making the change, will be described in the clinical study report (CSR). Additional exploratory analyses of the data will be conducted as deemed appropriate.

10.2.1.1. Missing Data Imputation

- Nonresponder imputation (NRI): All subjects who discontinue the study or the study treatment at any time for any reason will be defined as nonresponders for the analysis of categorical efficacy variables at discontinuation and subsequent visits. Subjects who receive rescue therapy will be analyzed as nonresponders at rescue and subsequent visits.
- MMRM: Continuous variables will be assumed to be missing after rescue or discontinuation for which an MMRM analysis will be performed.

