5.1. Overall Design

Study I9N-MC-FCAB (FCAB) is a Phase 2, multicenter, randomized, double-blind, placebo-controlled, parallel-group, outpatient study evaluating the efficacy and safety of LY3375880 SC 600 mg Q4W, 150 mg Q4W, and 50 mg Q4W as compared to placebo Q4W in adult subjects with moderate-to-severe AD. In addition, LY3375880 300mg Q4W will be evaluated in the maintenance period as described below.

The study duration will be up to 65 weeks over 4 study periods:

- Period 1: Screening Period lasting from 8 to 35 days prior to Week 0 (baseline, Visit 2).
- Period 2: Induction Period, lasting from Week 0 (baseline, Visit 2) through Week 16 (Visit 8).
- Period 3: Maintenance Period, lasting from Week 16 (Visit 8) through Week 52 (Visit 17, inclusive). At Week 16, the following will occur:
 - Responders (defined as having achieved a 50% reduction in the Eczema Area and Severity Index score [EASI-50] response, regardless of whether rescue therapy has been initiated) will undergo the following re-randomizations:
 - Subjects on any dose of LY3375880 will be re-randomized at a 2:1 ratio to either maintain their current regimen or to receive placebo until loss of response (not achieving a 25% reduction in the EASI score [EASI-25] at a scheduled visit), at which point they will restart their induction period regimen.
 - Subjects on placebo will continue receiving placebo until loss of response, at which point they will be reassigned to receive LY3375880 at 300 Q4W.
 - Nonresponders will undergo the following reassessments:
 - Subjects on 50 mg Q4W will be reassigned to 150 mg Q4W.
 - Subjects on 150 mg Q4W will be reassigned to 300 mg Q4W.
 - Subjects on 600 mg Q4W will remain on their current regimen.
 - Subjects on placebo will be reassigned to receive 300 mg Q4W.
 - Subjects with persistent disease activity, defined as not achieving EASI-25 for 3 consecutive scheduled maintenance period visits, not already on 600 mg Q4W will be reassigned to 600 mg Q4W for the remainder of the study.
- Period 4: Post-Treatment Follow-Up Period, spanning approximately 8 weeks from Week 52 (after Visit 17) to Week 60 (Visit 801).

Rescue therapy is permitted starting at Week 8 for subjects who do not achieve an EASI-25 response. Refer to Section [7.7.3](#) for details.

Treatment Arms and Duration:

[figure not shown]

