and frequency of administration in future studies. Nonresponders on LY3375880 on 50 mg and 150 mg will be reassigned to the next highest dose level to evaluate whether disease activity will respond to a higher dose of active study drug. Placebo nonresponders will be reassigned to 300 mg to efficiently obtain safety and efficacy data on the intermediate dose of 300 mg Q4W not tested in the induction period.

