7.7.3. Rescue Therapy

Rescue therapy is permitted **starting at Week 8** for subjects who do not achieve an EASI-25 response. If the subject meets criteria, the decision to implement rescue is according to investigator judgment and is not a requirement. Rescue therapy should only be initiated at a visit at which an EASI-25 is not met.

Choice of rescue therapy treatment

- Triamcinolone 0.1% cream and/or hydrocortisone 2.5% ointment. In the event where either of these topical formulations is not available, an alternate, equivalent potency TCS cream and/or ointment may be used.
- Investigators may also select to use TCNI and/or crisaborole where approved. If TCNI are prescribed, use should be limited to problem areas only (e.g., face, neck, skin folds, genital areas, etc.).
- On the days of study visits, topical therapy should not be applied before the subject has undergone all study procedures and clinical evaluations in order to allow adequate assessment of skin dryness.
- Subjects rescued to topical therapy will continue to take IP and use of rescue therapy will be documented in the eCRF.

In subjects who do not improve sufficiently with the prescribed provided rescue topical therapy after 7 days, a higher potency TCS may be used and IP may continue. It is recommended that if a subject reaches “clear” to “almost clear” skin after topical rescue, then medium- and/or high-potency TCS and TCNI should be stopped, and low-potency TCS (e.g., hydrocortisone 2.5% ointment) should be used once daily for an additional 7 days, then stopped. If lesions return, subjects can be retreated with TCS with or without TCNI and/or crisaborole as before at the discretion of the investigator.

If topical rescue therapy as described above fails to sufficiently control AD symptoms and if the investigator determines that a subject requires treatment with another therapeutic agent that has been demonstrated to be effective for treatment of AD but is contraindicated in this study, the subject should be discontinued from the study. In such cases, discontinuation from the study occurs prior to introduction of the new agent.

Note that subjects who receive rescue therapy during the induction period will be considered nonresponders for the primary analysis, but will undergo re-assignment/re-randomization at Week 16 based on EASI-50 response according to Section 5.1, and will not automatically be considered nonresponders for purposes of treatment assignment.

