### **5.4. Handling of Dropouts or Missing Data**

Nonresponder imputation (for categorical variables) and MMRM (for continuous variables) will be the primary methods used to handle missing data. Subjects who receive rescue therapy will be considered missing at rescue and all subsequent visits.

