#### **5.4.1. Nonresponder Imputation**

For the analysis of categorical efficacy and health outcomes variables such as IGA(0,1) and EASI50/75/90, the primary method to impute missing data will be a nonresponder imputation (NRI) method.

All categorical endpoints will utilize the NRI method to patients who permanently discontinued study drug or were rescued.

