#### **5.4.2. Mixed Model for Repeated Measures**

For the continuous secondary and exploratory efficacy and health outcome variables, such as EASI score and SCORAD score, MMRM analyses will be performed to mitigate the impact of missing data. This approach assumes that missing observations are missing-at-random (missingness is related to observed data) during the study and takes into account both the missingness of data and the correlation of the repeated measurements.

All continuous endpoints will utilize MMRM to patients who permanently discontinued study drug or who were rescued.

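### Rescue during induction fixes a subject as a Week 52 nonresponder, although it precedes the Week 16 re-randomisation or reassignment and is ignored when that assignment is made

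*Protocol*

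**What the plan says.** - **Categorical endpoints.** Protocol 10.2.1.1: "Subjects who receive rescue therapy will be analyzed as nonresponders at rescue and subsequent visits". SAP 5.4: "Subjects who receive rescue therapy will be considered missing at rescue and all subsequent visits". SAP 5.4.1: "All categorical endpoints will utilize the NRI method to patients who permanently discontinued study drug or were rescued". None of these limits the rule to a study period.
- **Continuous endpoints.** Protocol 10.2.1.1: "Continuous variables will be assumed to be missing after rescue or discontinuation for which an MMRM analysis will be performed". SAP 5.4.2: "All continuous endpoints will utilize MMRM to patients who permanently discontinued study drug or who were rescued".
- **When rescue can start.** Protocol 5.1: "Rescue therapy is permitted starting at Week 8 for subjects who do not achieve an EASI-25 response". It is topical, optional and stoppable, and subjects stay on study drug (Protocol 7.7.3).
- **What happens at Week 16.** Protocol 5.1 assigns maintenance treatment on observed EASI-50 and disregards rescue. Protocol 7.7.3 confirms that subjects rescued in induction "will not automatically be considered nonresponders for purposes of treatment assignment".
- **Maintenance sections.** Protocol 10.2.1.2 and SAP 5.2.2.2 cover baselines and (in the protocol) descriptive reporting. Neither resets the rescue rule.
- **What is analysed at Week 52.** Protocol 10.2.3.2 lists IGA 0 or 1 at Week 52 as a secondary analysis under the logistic model. SAP Table FCAB.5.2 has a secondary Week 52 IGA row in the maintenance population, comparing each dose, 300 mg included, with placebo.

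**The concern.** Counting rescue as failure is sound when rescue follows the assignment being evaluated, as it does for Week 16. For maintenance the order is reversed: induction rescue comes before the maintenance assignment, so it is a baseline characteristic of the subject and not an outcome of the maintenance regimen.

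A subject can be rescued at Week 8, stop the topical treatment, be given a new regimen at Week 16 and be clear at Week 52, yet still be scored a nonresponder. A rescued subject who reaches EASI-50 is re-randomised as a responder but scored a nonresponder in every maintenance response proportion.

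The rule probably bites hardest among Week 16 nonresponders, because only subjects below EASI-25 may be rescued. Protocol 5.4 moves nonresponders on the two lower doses upward "to evaluate whether disease activity will respond to a higher dose of active study drug". For each such subject already rescued, the Week 52 answer is set before the first dose of the new regimen.

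**Working it through.** **1. The plan's own figure.** Protocol 10 and SAP 5.1 claim at least 90% power for 36% versus 8%, 50 per arm, two-sided Fisher's exact test at 0.05. Exact enumeration over all outcome pairs gives 91.4%, so the claim reproduces. It is unaffected here, because induction rescue is nonresponse at Week 16 on any reading.

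**2. Order of events.** Rescue possible from Week 8; assignment at Week 16 on observed EASI; endpoint at Week 52. The nonresponse label set at the first step is never lifted at the second.

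**3. Formula.** For one maintenance group, let *r* be the share rescued in induction, *pN* the true Week 52 response rate in subjects not rescued in induction, and *pR* the rate in those who were. Leave aside rescue or discontinuation during maintenance, which is nonresponse either way.

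- True rate = (1 − r) × pN + r × pR
- Reported rate = (1 − r) × pN + r × 0
- Loss = r × pR
- Ceiling on the reported rate (pN = 1) = 1 − r

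**4. Numbers.** Neither *r* nor *pR* is in the documents; all values below are assumptions.

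| r | Ceiling | Loss, pR = 5% | Loss, pR = 10% | Loss, pR = 30% |
|---|---|---|---|---|
| 20% | 80% | 1 point | 2 points | 6 points |
| 40% | 60% | 2 points | 4 points | 12 points |
| 60% | 40% | 3 points | 6 points | 18 points |

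For example, 0.40 × 0.10 = 0.04 and 0.40 × 0.30 = 0.12.

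**5. Uneven effect.** Subjects assigned to placebo in maintenance are all Week 16 responders (Protocol 5.1), while reassigned groups start from nonresponders. *r* is therefore likely to differ between the groups set against each other in the Week 52 row of SAP Table FCAB.5.2. The rule shifts such a comparison by the difference between the two groups' values of r × pR.

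**The case against.** **Size.** A reader might multiply the true group rate by 1 − r. That assumes rescued subjects respond at Week 52 as often as the rest, which sits badly with rescue being confined to subjects below EASI-25. The loss depends on *pR*, which may be low. Rescue is also optional, so *r* may be small. This stands, and is why the table shows several values of *pR*.

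**Withdrawal comparison.** A reader might infer that the maintain-versus-withdraw contrast is diluted by a calculable amount. The documents do not support that. SAP Table FCAB.5.2 has no such responder-rate row. Protocol 10.2.3.3 gives loss and maintenance of response to Kaplan-Meier curves with no stated rescue rule. Withdrawn subjects also restart their induction regimen on losing response.

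**Continuous data.** A reader might infer that all continuous maintenance data after rescue are discarded. SAP 5.4 is broad enough to suggest it, but Protocol 10.2.1.1 ties missingness to MMRM analyses, and SAP Table FCAB.5.2 lists MMRM only at Week 16. Protocol 10.2.3.3 mentions the models for maintenance as well, so the position is unclear.

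**Status.** Protocol 10.2.1.2 calls maintenance exploratory and limits it to descriptive statistics, and SAP 5.6 applies no multiplicity control. This lowers the stakes. It does not remove them, because Week 52 IGA is still listed as secondary in both documents, and a descriptive proportion is capped all the same.

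**Intent.** Protocol 7.7.3 links nonresponder status after induction rescue to the primary analysis, which may hint at a narrower rule. It does not say the status lapses, and the general rules say the opposite.

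**Carry-forward is conservative.** A subject may reach EASI-50 because of topical steroid, and lifting the rule could credit study drug with that benefit. This is a fair reason to show both versions. It does not justify reporting only the version in which the outcome predates the assignment.

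**Conclusion.** The concern holds for the Week 52 IGA secondary proportion and for maintenance response proportions analysed with nonresponder imputation. Both are capped at 1 minus the share rescued in induction, most likely in the reassigned nonresponder groups. The loss is 2 to 6 points for 20% to 60% rescued if *pR* is 10%, and 6 to 18 points if it is 30%. Both inputs are assumptions; small values of either make the loss small.

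A reader might conclude that maintenance results in general are settled before maintenance begins. The text does not support that. The primary analysis, its power and treatment assignment are untouched, and SAP 5.13 keeps post-rescue data in the safety analyses. For Kaplan-Meier curves and continuous maintenance summaries the governing rule is unclear, and no figure is claimed. The point should be corrected in the SAP, but it does not threaten the Week 16 conclusion.

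**What to change.** - Keep the current rule for Week 16.
- For Week 52 IGA and the maintenance categorical summaries, report an analysis in which only rescue started or still in use after the Week 16 assignment triggers nonresponder imputation, alongside the carry-forward version.
- State which rescue rule applies to the Kaplan-Meier analyses and to continuous maintenance summaries.
- Tabulate the number rescued in induction by maintenance group.
- Reconcile two passages on which the derivation depends: SAP 4.1 dates the re-assignment at Week 20 where Protocol 5.1 says Week 16, and the two documents send 150 mg nonresponders to different regimens.

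**Cost.** SAP wording, one derived flag and one extra set of tables. Rescue use is already recorded in the eCRF (Protocol 7.7.3); the flag also needs stop dates, which SAP 5.10 already relies on for concomitant therapy. Treatment does not change.

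**Downside.** Some residual benefit of early topical rescue may be counted as response; the carry-forward version beside it shows how much could be at stake.
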